4 STUDY POPULATION

The study population will consist of patients undergoing emergency surgery for a ruptured abdominal aortic aneurysm. Patients must meet all the inclusion criteria and none of the exclusion criteria to be enrolled in the study. The inclusion and exclusion criteria apply during screening and prior to administration of the first dose of study drug on D0.

4.1 Inclusion Criteria

To be eligible for inclusion into this study, each patient must fulfil the following inclusion criteria (alternatively 1 or 2 and all 3, 4 and 5) during screening and prior to randomisation and the first dose of study medication being administered on D0:

1. Patients (male or female) presenting with a RAAA diagnosed by ultrasound or CT-scan in the emergency room
 - all forms of infrarenal RAAAs with or without coexisting iliac aneurysms are included

or

2. Patients (male or female) presenting with symptoms of RAAA known to have an infrarenal AAA and proceeding straight to open repair without radiological assessment and rupture confirmed (retroperitoneal haematoma) intra-operatively

and

3. Aneurysma repair must be infra-renal, i.e. the proximal anastomosis must be below the renal arteries and the renal arteries must stay intact. Temporary above the renal clamping can be used for a maximum of 30 minutes (total clamping time)

and

4. Patients providing informed consent (written signed or witnessed)
Or their next of kin providing written informed consent
5. Age over 18 years

4.2 Exclusion Criteria

To be eligible for inclusion into this study, each patient must not meet any of the following exclusion criteria **during screening or prior to randomisation and the first dose of study medication being administered:**

1. Moribund patient not eligible for treatment in ICU or expected to survive surgery
2. Markedly short life expectancy, e.g. advanced malignant disease
3. Current participation in another experimental treatment protocol
4. Significant congestive heart failure, defined as New York Heart Association (NYHA) class IV
5. Current treatment with IFN alpha or IFN beta

6. Dialysis therapy for chronic renal failure
 7. Irreversible shock from haemorrhage
 8. Unconsciousness when arriving to the hospital and during screening
 9. rEVAR first (prior attempt for endovascular aortic repair for current rupture, prior elective EVAR applicable)
 10. Earlier diagnosed cirrhosis in medical records
 11. Pregnancy and women with child bearing potential without negative blood pregnancy test
 12. Rupture not confirmed by CT or intra-operatively (impending ruptures are excluded)
 13. RAAA requiring repair of the renal arteries or the proximal aorta
 - thoracoabdominal aneurysms requiring immediate repair
 - damaged renal arteries during emergency clamping requiring repair
- NOTE:**
- temporary clamping above the renal arteries (max 30 min total clamping time above the renal arteries) **does not** lead to exclusion
 - ligation of the left renal vein **does not** lead to exclusion

4.3 Confirmation of Patient Eligibility

To ensure appropriate enrolment into the study there will be a formal confirmation of eligibility process utilising the following procedure:

There will be an electronic Case Report Form (eCRF) checklist of inclusion and exclusion criteria; all items will need to be ticked correctly. The Clinical Data Management System (CDMS) will not allow a patient to progress to randomisation if these have been completed incorrectly. The vascular surgeon will perform this procedure and randomization immediately after the operation. If the ticks correspond to the inclusion criteria, the CDMS will make the patient available to be randomised.

If the ticks are against inclusion, the patient cannot be randomised and the reason for this will be noted in the eCRF, and the patient will be regarded as a screening failure.

With this method, only those patients whose data are recorded as meeting eligibility criteria can be randomised.

4.4 Patient Withdrawal and Replacement

4.4.1 Discontinuation Criteria

Patients may discontinue from the entire study, including follow-up, at any time without any reason and without prejudice to their future medical care; they are not obliged to state their reasons for withdrawing.

Additionally, the Investigator may discontinue a patient at any time if it is considered to be in the best interest of the patient. Discontinuation of study medication by the Investigator due to improvement of a patient's condition **does not** constitute a withdrawal as the patient will continue with the study assessments.

A patient **may be discontinued** from the study for example of the following reasons:

- Protocol violations including non-compliance with study procedures or patient lost to follow-up
- SAEs
- Administrative reasons
- Patient request
- Sponsor request
- Investigator request
- Authority request

In the case of a discontinuation, the Investigator must ensure that the status page in the eCRF for the **end of the study** is completed.

Patients may be required to **discontinue from study drug** after discussion with the Sponsor and/or Investigator for the following reasons:

- AEs
- At the discretion of the Investigator or if it is considered to be in the patient's best interest

If the administration of study medication is prematurely discontinued, the primary reason for discontinuation must be recorded in the appropriate section of the eCRF and all efforts made to complete the observations on that study treatment day as thoroughly as possible.

A complete final evaluation following the patient's discontinuation should be made on the day of the discontinuation/discharge, as described in Section 7.2. and any ongoing AEs should be followed up to resolution or study D30, whichever occurs first.

The study will be terminated if, in the opinion of the Sponsor, significant safety concerns arise during the conduct of the study.

Patients who discontinue study drug may continue in the study. The Investigator must ensure that the status page in the eCRF for the end of study is completed.

In all cases, the reason(s) for discontinuation, including the primary reason, must be recorded in the eCRF. If a patient prematurely discontinue from the study drug for any reason, the Investigator must make every effort to perform the evaluations described for the follow-up visits. Any on-going AEs should be followed up to resolution or D30 whichever is the sooner. See also Section 7.6.1. A permission will be sought to access the patient's medical records for data relevant to the study (e.g., mortality, VFDs, etc.) to complete the D30 and D90 follow up. See also section 9.6.2.

Patients who withdraw consent for their data to be analysed will be identified in the CDMS. Any data collected will not be deleted, but will not be used in any subsequent outputs.

Patients that have received at least one dose of the study drug and discontinued will not be replaced.

The study will be terminated if, in the opinion of the IDMC or the Sponsor, significant safety concerns arise during the conduct of the study.

4.4.1.1 Non-attendance of Follow-up Assessments

Attempts should be made to contact patients discharged from hospital who do not attend their study follow-up assessments to ensure their well-being. In such cases, the

patient will be contacted at least twice by telephone and once by letter to request that they attend the scheduled follow-up assessment. If patients do not respond they will be considered as *lost to follow up* at that time point. If a patient is lost to follow-up, wherever possible mortality data will be sought at all remaining mortality time points from alternative sources such as the patient's local physician.

4.4.2 **Replacement Policy**

All patients who become ineligible after consenting but before randomisation are replaced and deemed as screening failures. A screening failure is defined as any patient who does not comply with the inclusion and exclusion criteria during screening **or** prior to randomisation and receiving the first dose of study medication.

Patients who complete screening and are randomised and receive at least 1 dose of the study medication will not be replaced even if later withdrawn or lost to follow up.

4.5 **Planned Sample Size and Number of Study Centres**

It is planned to randomise 152 patients at 10-18 hospital study centres in Finland, in UK, in Lithuania and in Estonia and possibly in other countries in EEA and in USA for this study. Possible additional selection will be decided later, as required. See Section 8.2. for a discussion of sample size.

4.6 **Patient Randomisation**

4.6.1 **Randomisation Scheme**

Patients are randomly assigned to treatment with FP-1201-lyo or placebo in the randomisation ratio of 2:1 (active:placebo) for treatment groups, stratified by sex and age.

The treatment assigned to each patient is determined according to a computer-generated randomisation list within eCRF.

4.6.2 **Randomisation of Patients to Treatment**

Randomisation of patients to treatment will occur immediately after completion of surgery and after all screening procedures have been performed and eligibility for inclusion in the study has been confirmed. Each randomised patient will receive a unique randomisation number. Randomised patients who terminate their study participation for any reason, regardless of whether study drug was taken or not, will retain their randomisation number.

The Investigator will use IWRS for randomisation of patients. Details can be found in the study file.

5 STUDY DRUG

5.1 Identity

RentschlerBiopharma SE, Laupheim, Germany manufactures lyophilised FP-1201-lyo (recombinant human IFN beta-1a) and the matched placebo. Both FP-1201-lyo and placebo powders are free of animal serum and human serum albumin. Vetter Pharma International Services, Ravensburg, Germany manufactures pre-filled water for injection (WFI) diluent syringes.

A MixJect® transfer device will be used in this study. This MixJect® transfer device is a single unit for reconstituting a powdered drug with a diluent pre-filled syringe. Upon reconstitution, the drug is available for immediate injection. The MixJect® transfer device enables the safe, rapid and easy preparation of lyophilised drugs. The MixJect® transfer device is manufactured by West Pharmaceutical Services GmbH, Germany/Ra'anana, Israel. The device carries the CE mark and has 510(k) approval by the United States Food and Drug Administration.

PCI, UK, is responsible for the packaging of FP-1201-lyo and matched placebo in a carton box. The pre-filled WFI diluent syringe, the MixJect® transfer device and the reconstitution instructions are packaged in the accessorial carton kit. PCI, UK or Ireland, is responsible for distributing the investigational medicinal product to the study sites.

5.2 Administration

FP-1201-lyo 10 µg (or placebo) will be diluted in WFI near the patient/in the ICU. Once prepared, the dose must be administered to the patient immediately. The diluted FP-1201-lyo or placebo will be administered as an intravenous bolus injection via a central or peripheral line. The injection will be followed with a 5 mL flush of sterile saline (not provided).

Study drug injections will be given once daily for 6 days. The injection should be given at the same time each day ± 1 hour providing the patient's condition allows this. If for any reason this is not possible, the treatment window may be extended by up to 4 hours i.e. ± 2 hours. The reason for the delay must be entered in the eCRF. Subsequent doses should not be delayed and should revert to the original time schedule (e.g., if the D1 dose was at 13:00, the D2 dose was delayed and given at 15:00, the D3 dose should be given at 13:00 ± 1 hour).

No dose modifications or temporary cessations of study drug administration are allowed. If a delay beyond the 4-hour window described above is required, the patient must be withdrawn from study drug but all data must continue to be collected per protocol. Administration of a second course of study drug is not permitted.

The first dose of study medication is administered when the patient has arrived at the ICU after successful infra-renal aortic repair with intact renal arteries given the patient is viable. A prior temporary proximal aortic clamp (total maximum clamping time of 30 min) may be used to assess and control the operative situation. Surgical re-intentions (e.g. bleeding, lower limb embolia, intra-abdominal pressure and open abdomen, bowel resection) do not lead to exclusion if the study drug is administered as scheduled and the re-intentions do not violate the inclusion criteria, i.e. re-doing the upper anastomosis to the renal arteries or above.

5.3 Packaging, Labelling and Storage

Study drug, i.e. FP-1201-lyo or matched placebo, is packaged in a carton. The pre-filled WFI diluent syringe and the MixJect® transfer device are packaged in an accessorial carton kit.

Six investigational medicinal products and six accessorial carton kits are reserved for each patient to cover the 6-day treatment period.

Labelling will be prepared by PCI to meet the local regulatory requirements.

All study drug supplies must be stored in accordance with the manufacturer's instructions, i.e., FP-1201-lyo/placebo is to be stored at 2-8°C and the accessorial carton kits are to be stored at room temperature. Until dispensed to the patients, the study drug will be stored in a securely locked area, accessible to authorised personnel only.

The investigational medicinal product and the accessorial carton kits are dispensed only by the Investigator or by a member of staff specifically authorised by the Investigator, or by a pharmacist, as appropriate.

5.4 Blinding and Breaking the Blind

The study will be performed in a double-blind manner. All study drugs will be supplied in identical vials and will be similar in colour and appearance, thereby enabling double-blind conditions.

The treating physician (investigator) is responsible for the medical care of the trial patient and the study set up allows the investigator to rapidly break the treatment code in case of an emergency.

The study blind should only be broken in a medical emergency (where knowledge of the study drug received would affect the treatment of the emergency) or as a regulatory requirement (e.g., for SAEs or death). Note that there is no specific antidote or method of removing the study drug from the body (such as dialysis) and the best available care for the patient should be continued.

If the blind is broken, the date, time and reason must be recorded in the patient's eCRF and any associated AE report. It is the responsibility of the investigator to promptly document and explain any unblinding to the sponsor/CRO.

Detailed instructions for the use of the IWRS in order to break the study blind for a patient are provided in a separate document that will be filed in the Site File and Trial Master File. As well as the IWRS, a backup system enabling unblinding of treatment is provided to the sites.

After a patient has been unblinded data collection should continue as per protocol.

Suspected unexpected serious adverse reactions (SUSARs), which are subject to expedited reporting, should be unblinded before submission to the regulatory authorities and Independent Ethics Committees (IECs).

The overall randomisation code will be broken only for reporting purposes (for interim and final analyses). This will occur once all D90 clinical data have been entered into the database and all data queries have been resolved, and the assignment of patients to the analysis sets has been completed. The randomisation code will be opened for the interim analysis, which is performed when at least 31 patients have been enrolled and the D30 clinical data is available.

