6.2.6 Days in hospital and/or other health care unit

The length of a patient's hospital stay will be assessed by:

- the number of days the patient stayed in hospital at D30 and D90
- the number of days the patient stayed at another primary or rehabilitating health care unit after hospital discharge at D30 and D90.

6.2.7 *Days on haemodialysis*

The number of days on haemodialysis will be assessed at D30 and D90. Haemodialysis at D90 is considered permanent.

6.2.8 *Prevalence of compartment syndrome as measured by intra-abdominal pressure (IAP)*

Intra-abdominal pressure (IAP) is routinely measured during ICU stay via urine bladder catheter. IAP is recorded daily and a comparison of IAP between study groups is made.

6.3 **Safety Variables**

6.3.1 *Adverse Events*

6.3.1.1 *Collection of Adverse Events*

It is the responsibility of the Investigator to collect all AEs (both serious and non-serious) derived by observation, by spontaneous unsolicited reports of patients, and, where appropriate, by routine open questioning, e.g., “How have you felt since I last saw you?”

6.3.1.2 *Definitions*

Definitions of AEs and SAEs and their documentation and reporting within this study follow International Conference on Harmonisation (ICH) Good Clinical Practice, European Union, and national regulations and requirements (Clinical safety data management 1994).

An AE is defined as any untoward medical occurrence that occurs in a patient or clinical investigation subject administered a pharmaceutical product, and which does not necessarily have to have a causal relationship with this treatment. An AE can therefore be any unfavourable and unintended sign (including an abnormal laboratory finding), symptom or disease temporally associated with the use of an investigational product, whether or not it is considered related to the product.

All AEs up to D30 are collected. All AEs up to D30, which lead to death, are reported as SAEs. However, all deaths up to D90 will be reported as SAEs. Concomitant illnesses, which existed before entry into the study, will not be considered AEs unless there is any deterioration from baseline that is considered clinically relevant or significant during treatment or follow-up period until D30 or discharge from ICU. All AEs must be documented, regardless of the source of identification (e.g., physical examination, laboratory assessment, ECG, reported by patient).

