6.3.1.3.1 Seriousness

An SAE is defined as any untoward medical occurrence that at any dose:

- Results in death
- Is life-threatening. This means that the patient is at risk of death at the time of the event. It does not mean that the event hypothetically might have caused death if it were more severe
- Requires inpatient hospitalisation or prolongation of existing hospitalisation
- Results in persistent or significant disability or incapacity
- Is a congenital anomaly or birth defect
- Is an important medical event that may not be immediately life-threatening or result in death or hospitalisation but that may jeopardise the patient or require intervention to prevent one of the above outcomes. Examples of such events are intensive treatment in an emergency room or at home for allergic bronchospasm; blood dyscrasias or convulsions that do not result in hospitalisation; or development of drug dependency or drug abuse

“At any dose” does not imply that the patient is receiving study treatment at the time of the event. Study drug doses may have been given during treatment cycles or interrupted temporarily prior to the onset of the SAE, but may have contributed to the event.

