8.5 Evaluation of efficacy

8.5.1 *Evaluation of primary efficacy endpoint*

The primary endpoint of the study will be:

- All-cause mortality at D30

To be eligible for efficacy analysis each patient must receive at least two doses of the study medication with an effect time of 12 hours after second dose. This means that a death within 36 hours from the first dose of study treatment leads to exclusion from efficacy analysis. This derives from the fact that based on the prior clinical phase I/II studies with interferon beta-1a, its effect on the expression of CD73 and production of adenosine will require 12 to 24 hours from administration of the drug. Thus, therapeutic levels will not be reached until 12 hours from the second dose, i.e. 36 hours from the first dose. Measuring efficacy against multi-organ failure prior to this point is misleading because therapeutic levels have not yet been reached.

The efficacy analyses will be conducted using logistic regression model for the observed mortality rates in the two treatment groups. Stratification factors used in the randomisation will be included in the model. Primary result will be presented as an adjusted odds ratio and a 95% CI for the adjusted odds ratio. Also, a 95% confidence interval (CI) for the difference in the observed mortality rates will be calculated. A two-sided significance level of 0.05 will be used for all analyses.

There will additionally be an evaluation of the homogeneity of the treatment effect by investigating treatment by centre and treatment by baseline factor interactions in the logistic model. Data for the primary efficacy endpoint will also be presented for key, pre-defined subgroups of patients together with 95% CIs for the difference in those rates to supplement the investigation of homogeneity. Mortality at D30 will be illustrated also using survival function and Kaplan-Meier curves including log-rank test as an exploratory analysis.

8.5.2 *Evaluation of secondary efficacy endpoints*

By way of further confirmatory measures of efficacy, the following endpoints will be analysed:

- Time and reason/diagnosis of death up to D90 (3 months)
- Number of VFDs up to D30
- Number of days receiving hemodialysis at D30 and D90
- Number of ICU free days up to D30
- Organ failure free days up to D30
- Neutralizing antibodies IFN beta (NAbs) in whole blood samples up to D30
- Number of days in hospital up to D30 and D90 (length of stay in another health care facility)

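### Protocol 5.4 names SAEs and death as examples of a regulatory ground for breaking the blind; these examples are too broad in a trial whose primary endpoint is death, and no firewall is stated

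*Protocol*

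**What the plan says.** Protocol 5.4 gives two grounds for an individual code break. The first is "The study blind should only be broken in a medical emergency", where knowing the treatment would affect care. The second is "or as a regulatory requirement (e.g., for SAEs or death"). The parenthesis does not limit its examples to related, unexpected or expedited events.

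Later in 5.4 a specific instruction covers SUSARs, which "should be unblinded before submission to the regulatory authorities and Independent Ethics Committees (IECs"). Protocol 6.3.1.7 defines a SUSAR as serious, associated with study drug and unexpected. On the full list, 5.4 says: "The overall randomisation code will be broken only for reporting purposes (for interim and final analyses").

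Sites can unblind through the IWRS or a backup system. The date, time and reason go into the eCRF and any associated AE report, and the investigator explains the break to the sponsor or CRO.

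The primary endpoint in Protocol 8.5.1 is "All-cause mortality at D30". Protocol 6.3.1.3.1 lists "Results in death" among the criteria for an SAE, and 6.3.1.2 adds: "However, all deaths up to D90 will be reported as SAEs". The SAP does not discuss individual code breaks, and its data listing plan (19.4) has no listing for them.

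**The concern.** The examples attached to the regulatory ground take in the primary endpoint itself. A site that follows them could open the code when a patient dies, or when a living patient has an SAE, and could believe that it is following the protocol. Section 5.4 names no unblinded safety function and does not say that the site, sponsor study team or CRO stay blind to the result.

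Four things are at stake:
- **Emerging effect.** With 2:1 allocation known, the arm split of unblinded deaths gives information on the primary comparison. That would come outside the interim analyses of Protocol 8.6 and the IDMC's unblinded review in 9.8.
- **Causality.** The investigator judges relatedness (6.3.1.3.3), and that judgement feeds SUSAR status. A code opened because the event is an SAE may come before the judgement and influence it.
- **Blind review.** Membership of the PPS is to be settled at a blind review (Protocol 8.1). SAP 8 leaves the subject classification to be signed before database lock.
- **Living patients.** If the code is opened after an SAE, later investigator decisions for that patient, such as stopping study drug for improvement (Protocol 3.1), are made with knowledge of treatment. Ventilator-free and ICU-free days could be affected.

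**Working it through.** **1. Do the examples reach the primary endpoint?** The primary event is death from any cause by D30 (8.5.1). A fatal event is an SAE (6.3.1.3.1), and all deaths to D90 are reported as SAEs (6.3.1.2, repeated in 6.3.1.4 and 6.3.1.5). So every primary event is both a death and an SAE, and matches both named examples.

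**2. What regulatory unblinding do the documents require?** Only that of SUSARs (5.4), which must be serious, drug-associated and unexpected (6.3.1.7). No section requires unblinding of an unrelated or expected death. The examples are therefore wider than the only requirement that the documents describe.

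**3. Does the sentence on the overall code settle it?** No. It governs the full randomisation list. Individual code breaks fall under the two grounds above.

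**4. The plan's own sample size.** Inputs from Protocol 8.2: 37% placebo, 15% active, 2:1 allocation, 80% power, two-sided 0.05, 129 evaluable (86 + 43), 15% early deaths, 152 randomised.
- Pooled proportion: (0.37 + 2 × 0.15)/3 = 0.2233.
- Placebo n = [1.96 √(0.2233 × 0.7767 × 1.5) + 0.8416 √(0.37 × 0.63 + 0.15 × 0.85/2)]² / 0.22² = 43.9, so 44 placebo and 88 active, 132 in all. Power at 43 + 86 is 0.792. This agrees closely with 129 and 80%.
- 129/0.85 = 151.8, rounded up to 152, as stated.

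**5. Deaths that the examples could cover, on those assumptions.**

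| Evaluable | Placebo | Active | Primary events |
|---|---|---|---|
| 35 (first interim, per SAP) | 11.67 × 0.37 = 4.3 | 23.33 × 0.15 = 3.5 | 7.8 |
| 129 (planned final) | 43 × 0.37 = 15.9 | 86 × 0.15 = 12.9 | 28.8 |

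Early deaths at full size: 152 − 129 = 23. These are also deaths and SAEs, but they are excluded from the primary analysis and are not primary events. Deaths between D30 and D90 and non-fatal SAEs are not counted, because the documents give no rate for them.

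**6. What the arm split would show.** With no treatment effect, 2/3 = 67% of evaluable deaths would be on active. Under the design assumptions the share is 12.9/28.8 = 45%, a gap of 22 percentage points. The standard error of the share around 67% is √(0.667 × 0.333/28.8) = 9 points with 28.8 events and √(0.667 × 0.333/7.8) = 17 points with 7.8. If all deaths were unblinded, the split would be informative at full size and only weakly so at the stage where the study stopped.

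**The case against.** The strongest reply is that 5.4 keeps the limiting words. The blind is to be broken only in an emergency or where a regulatory requirement applies; SAEs and death illustrate where one might arise and are not grounds of their own. A reader might infer that every death qualifies for unblinding. The text does not support that, because a requirement must still exist. This stands, and it limits the point to examples that are too broad. It does not make them harmless: they name the endpoint, and the only stated requirement is much narrower.

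A reader might also infer that the second ground contradicts the sentence on the overall code. It does not, since that sentence concerns the whole list. A general permission followed by a SUSAR instruction is loose drafting.

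Other inferences also fail:
- **Combined death count.** The 28.8 primary events and 23 early deaths should not be added and called primary events.
- **D90 mRS.** A patient who has died scores 6 by definition, so unblinding that death cannot bias that patient's score.
- **Guessing the next assignment.** Stratification is by sex and age, no centre stratum or block size is stated, and 10-18 centres were planned. Predictability cannot be established.
- **Sponsor's running count.** Date, time and reason must be recorded and the break explained. Nothing requires the allocation to be passed on.

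Finally, controls may exist in the separate IWRS instructions, the Safety Management Plan or the IDMC charter, which the protocol mentions but which are not among the documents reviewed. That is fair, and it is why no claim is made about what sites did.

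**Conclusion.** The point holds as a drafting fault with a real but bounded risk. Protocol 5.4 attaches to its regulatory ground two examples that cover every primary event, while the only concrete regulatory rule covers SUSARs, and neither document states a firewall around individual code breaks.

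The exposure is about 28.8 primary events in 129 evaluable patients, or about 7.8 in 35, plus about 23 early deaths in 152 randomised. These figures rest on the protocol's 37%, 15% and 15% assumptions. They count deaths that the examples could cover; the number of codes that would be opened cannot be estimated from the documents, and nothing shows that any were.

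Mortality is objective and the patient has already died when the death example could apply, so bias in that patient's own primary outcome is small. The risk lies in knowledge of the emerging split, causality judgements, the blind review, and decisions for living patients unblinded after an SAE. The study stopped after the first interim (SAP 2), so the wording change now serves mainly as a correction for later use, while a listing of code breaks remains useful for the report. Sample size, alpha and power are unaffected.

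**What to change.** In Protocol 5.4:
- Delete the parenthesis that names SAEs and death.
- State that regulatory unblinding is confined to SUSARs and is done by the existing pharmacovigilance function, with the site and the sponsor study team kept blind to the result.
- State that a death or an SAE is not in itself a reason to break the code.
- Leave the medical-emergency ground unchanged.

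In SAP 19.4, add a listing of all individual code breaks by arm, date and reason. The date, time and reason are already required in the eCRF, and the arm can be added from the randomisation list at reporting. If there were none, the report should say so.

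The cost is a short wording change in the protocol, matching lines in the site instructions and Safety Management Plan, and one listing. Emergency access to the code is unaffected.
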